### 1.3 Alpha-1-Antitrypsin

Few side effects and promising efficacy are desirable properties in an agent to be tested for GVHD preemption. Alpha-1-antitrypsin (AAT, A1PI, Glassia®) possesses these properties. Glassia is a stable, liquid, ready to use preparation of 2% human AAT that belongs to the family of serine protease inhibitors and is primarily produced in the liver and secreted into the circulation. In addition to its anti-protease activity, A1PI has anti-inflammatory, anti-apoptotic and immunomodulatory properties.

Glassia is an injection solution prepared from pooled human plasma collected from healthy volunteers in accordance with Food and Drug Administration (FDA) and European Medicines Agency (EMA) regulations. It was approved in the United States (US) in July 2010 for chronic augmentation and maintenance therapy in adults with clinically evident emphysema due to severe hereditary deficiency of AAT.

The mechanism of action of AAT for GVHD is not fully understood. However, animal studies provide strong evidence to support AAT's use in this setting. GVHD results when donor T cells are primed against host antigens in the context of a pro-inflammatory environment (e.g., high pro-inflammatory cytokines such as IL-1, TNF and IL-6, low anti-inflammatory cytokines such as IL-10, and decreased regulatory T cell numbers). First, the administration of exogenous AAT significantly reduced the incidence and severity of GvHD in murine bone marrow transplant models. In one of these mouse GVHD models, Tawara et al showed that AAT administration before GVHD developed inhibited pro-inflammatory cytokine production, enhanced IL-10 production, and favorably altered regulatory T cell numbers. These findings were confirmed in a separate murine study by Marcondes et al which developed evidence that AAT alters mitochondrial biogenesis in a cell-specific manner. Specifically, AAT exposed effector T cells (which cause GVHD related tissue damage) have significantly less respiratory reserve than T-reg and DCs. These cell specific differences favor survival of immune cells that promote tolerance. Taken together, these data

show that AAT alters metabolism within immune system cells in an pro-tolerance, anti-inflammatory direction which supports its use in this trial of GVHD prevention.

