#### **Secondary endpoints:**

1. Overall survival at 6 months
2. Cumulative incidence of NRM at 6 months and 1 year
3. Relapse rate (see section 2.2.1)

4. 100 days incidence of clinically relevant GVHD states including steroid-refractory GVHD, grade II-IV GVHD, and grade III-IV GVHD (See section 2.2.1).
5. For patients who develop GVHD prior to day 100 post-HCT, the overall response rate (CR + PR) 28 days after initiation of systemic steroid treatment. PR is defined as improvement in one or more organs involved with GVHD symptoms without progression in others. For a response to be scored as PR on day 28, the patient must be in PR on day 28 and have had no intervening systemic therapy for acute GVHD other than steroids.
6. Cumulative incidence of severe GI GVHD stage 3 or 4 by day 100 post-HCT
7. Cumulative incidence of chronic GVHD requiring systemic steroid treatment by one year
8. Number of serious infections (defined as grade 3 by the Blood and Marrow Transplant Clinical Trials Network)

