### 3.2 Exclusion Criteria

- 3.2.1 Patients who develop acute GVHD prior to start of study drug
- 3.2.2 Patients at very high risk for relapse post HCT as defined by very high disease risk index
- 3.2.3 Patients participating in a clinical trial where prevention of GVHD is the primary endpoint
- 3.2.4 Uncontrolled active infection (i.e., progressive symptoms related to infection despite treatment or persistently positive microbiological cultures despite treatment or any other evidence of severe sepsis)
- 3.2.5 Patients who are pregnant
- 3.2.6 Patients on dialysis within 7 days of enrollment
- 3.2.7 Patients requiring ventilator support or oxygen supplementation exceeding 40% FiO2 within 14 days of enrollment.
- 3.2.8 Patients receiving investigational agent within 30 days of enrollment. However, the Principal Investigator (PI) may approve prior use of an investigational agent if the agent is not expected to interfere with the safety or the efficacy of alpha-1-antitrypsin
- 3.2.9 History of allergic reaction to alpha-1-antitrypsin

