The preliminary data for this study was generated from patients transplanted at multiple centers with heterogeneous GVHD treatment practices. In order to develop “real world” experience in this study, institutional GVHD treatment practices are permitted unless their use is explicitly prohibited.  
  
Patients who develop GVHD will be treated as per institutional standards with systemic and non-systemic treatments such as topical steroids or non-absorbable steroids for GI GVHD. If systemic steroid treatment is initiated the recommended starting dose is **prednisone 2 mg/kg/day**. Centers may use a starting dose of 2 mg/kg of methylprednisolone if that is their institutional practice. Additional agents for the purpose of treating GVHD (e.g., etanercept, extracorporeal photopheresis, ATG) are not allowed. The initiation of systemic GVHD treatment beyond continuation or adjustment of GVHD prophylaxis medications (see section 5.1.6) and corticosteroids will be considered the initiation of second line GVHD treatment and considered a treatment failure. **Study treatment with alpha-1-antitrypsin continues during GVHD treatment until all 16 doses have been administered or ten weeks have elapsed from the start of AAT, whichever comes first.**

GVHD treatment will be tapered according to local institutional tapering practices. A recommended taper is provided in the appendices.

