### 7.1.2 Proportion of CR and CR+PR

CR and PR on day 28 are scored in comparison to the patient's acute GVHD staging on the day systemic steroid treatment began.

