## 11.0 STATISTICAL CONSIDERATIONS

### 11.1 Study Design/Study Endpoints

This is a proof of concept pilot single arm, open label multicenter clinical trial. The primary study measure of efficacy is the incidence of steroid-refractory GVHD by Day 100 after HCT. GVHD is defined as steroid refractory if CR or PR is not achieved by day 28 of systemic steroid treatment **OR** if additional immunosuppression beyond steroids was given for treatment of GVHD prior to 28 days of steroid treatment. Subjects who start treatment for GVHD within 28 days of Day 100 (i.e., on or after Day 72 post-HCT) must be followed for a full 28 days of systemic steroid treatment for the purposes of assessing the primary study measure of efficacy.

Because we expect improvements in the incidence of steroid refractory GVHD to translate into better long-term outcomes, secondary endpoints include 6 month NRM and 6 months overall survival. Additional secondary endpoints related to efficacy will include, in subjects who develop GVHD, time to discontinuation of steroid therapy, number of lines of GVHD therapy, and cumulative incidence of chronic GVHD. Secondary endpoints related to safety include 6 month and 1 year relapse rates and incidence of serious (BMT CTN grade 3) infections by day 100.

The historical control population for this study consists of patients who met the criteria for a high MAGIC GVHD risk score at either day 7 and 14 (see Background).

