### 11.3 Data Analyses Plans

The primary endpoint is incidence of steroid-refractory GVHD by day 100. Death, lack of GVHD response to systemic steroids by day 28 of treatment, or initiation of additional systemic immunosuppressive therapy for GVHD will be considered failures for this

endpoint. The incidence of steroid-refractory GVHD by day 100 in the study patients will be compared to the historical control rate of 28%.

Secondary outcomes such as the overall response rate (CR+PR), the incidence of severe GI GVHD (stage 3 or 4), non-relapse mortality, relapse rates, overall survival, will be estimated and compared to historical controls.

Continuous variables will be summarized using standard summary statistics such as number of observations (n), mean, standard deviation (SD), minimum and maximum values, median, and 1st and 3rd quartiles. Categorical variables will be summarized in frequency tables as counts and percentages.

Cumulative incidence of non-relapse mortality will be estimated by Gray's method and relapse will be considered as a competing risk. Disease free and overall survival, defined as the time from the transplantation to death or to last follow-up if alive, will be estimated by the method of Kaplan-Meier and the probability curves and 95% confidence intervals will be provided based on the method of Brookmeyer and Crowley.

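### The day-28 steroid response rate is compared with historical controls only among patients who develop GVHD, a subset formed after AAT starts, so the two groups are not comparable and a true benefit could look like a loss

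*Combined protocol and SAP*

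**What the plan says.** Section 2.3, under secondary endpoints, restricts the response endpoint: "For patients who develop GVHD prior to day 100 post-HCT, the overall response rate (CR + PR) 28 days after initiation" of systemic steroids. Section 7.1.2 scores response against "acute GVHD staging on the day systemic steroid treatment began".

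Section 11.3 opens its list with "Secondary outcomes such as the overall response rate (CR+PR" and says that these outcomes "will be estimated and compared to historical controls". The list is introduced as examples, so it is open-ended. Section 11.1 adds two more measures confined to subjects who develop GVHD: time to stopping steroids and number of lines of GVHD therapy.

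The controls are defined by risk score alone: "The historical control population for this study consists of patients who met the criteria for a high MAGIC GVHD risk score". The documents give no response rate and no GVHD incidence for them.

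Two design features fix the timing. Section 3.2 excludes "Patients who develop acute GVHD prior to start of study drug", so every patient who enters the GVHD subset does so after AAT has begun. Section 5.1.7 adds: "Study treatment with alpha-1-antitrypsin continues during GVHD treatment until all 16 doses have been administered" or ten weeks have passed. The plan states no adjustment for this, no version of the response rate over all patients, and no statement that the rate is descriptive only.

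**The concern.** A response rate among patients with GVHD is a natural endpoint when treatment starts at GVHD diagnosis. Here treatment starts earlier, so developing GVHD is itself an outcome of treatment. Section 1.3 supports AAT partly because "the administration of exogenous AAT significantly reduced the incidence and severity of GvHD in murine bone marrow transplant models". If that carries over to patients, AAT changes both how many patients are in the denominator and which ones. The historical GVHD cases went through no such filter.

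A difference in response rate then mixes two things: a selection effect (which cases AAT prevented) and any direct effect of continued AAT on response to steroids. The data cannot separate them. If AAT prevents proportionally more steroid-responsive than refractory GVHD, the remaining cases are harder to treat and the rate falls although patients benefited. The opposite pattern can make the rate look better than the truth. What is at stake is the reading of one pre-planned secondary comparison in a study meant to guide further development.

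**Working it through.** **Inputs from the documents.** Section 11.2: historical SR GVHD by day 100 is 28%, target with AAT 15%, N = 30, go rule 6 or fewer SR cases, one-sided target significance 0.23, power 85%. Section 1.1: acute GVHD in 40% to 60% of transplant patients in general. That range is used only to choose assumed incidences; it is not a figure for high-risk patients.

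**The plan's own figure.** Exact binomial, n = 30: P(X ≤ 6 | 0.28) = 0.224 and P(X ≤ 6 | 0.15) = 0.847. The stated 85% power is reproduced. The attained level of 0.224 lies just under the 0.23 target, as expected for a discrete test. The plan gives no sample size, power or control value for the response-rate comparison.

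**Response rate as a function of two incidences.** Section 7.1.3 makes non-response at day 28, or added systemic immunosuppression before then, the definition of SR GVHD. Let S be the incidence of SR GVHD and G the incidence of steroid-treated GVHD. Then, approximately,

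response rate = 1 − S/G.

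This treats every GVHD case as steroid-treated and ignores deaths before day 28, so the percentages are illustrative.

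**When the sign reverses.** Write G0 and G1 for GVHD incidence in controls and with AAT. At the protocol's effect, the AAT rate falls below control when

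1 − 0.15/G1 < 1 − 0.28/G0, that is, G1/G0 < 0.15/0.28 = 0.536,

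which is a relative reduction in total GVHD of more than 46.4%. The break-even G1 is 21.4%, 26.8% or 32.1% for an assumed G0 of 40%, 50% or 60%.

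| Assumed GVHD, control → AAT | SR GVHD, control → AAT | Response, control | Response, AAT | Reading |
|---|---|---|---|---|
| 60% → 25% | 28% → 15% | 53.3% | 40.0% | looks worse, is better |
| 50% → 25% | 28% → 15% | 44.0% | 40.0% | looks worse, is better |
| 60% → 40% | 28% → 15% | 53.3% | 62.5% | right direction |
| 50% → 70% | 28% → 30% | 44.0% | 57.1% | looks better, is worse |

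In the first row, responsive GVHD falls from 60 − 28 = 32 to 25 − 15 = 10 per 100 patients, a 69% reduction (22/32), against 46% for refractory GVHD (13/28). In the third row it falls from 32 to 25, a 22% reduction (7/32). The reversal therefore needs AAT to prevent proportionally more responsive than refractory disease.

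**Same benefit without conditioning.** The share of patients free of SR GVHD moves from 72% to 85% in all of the first three rows, whatever the GVHD incidence.

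**Precision (a separate matter).** At an assumed GVHD incidence of 20% to 60%, 6 to 18 of 30 patients contribute. The exact 95% interval is 12% to 88% for 3/6 and 26% to 74% for 9/18.

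**The case against.** The strongest reply is that nothing turns on this rate. Section 11.2 has one go rule, the count of SR GVHD cases, and the response rate has no threshold, test or control value. The secondary objectives are framed as preliminary estimates, so the comparison may be meant as informal benchmarking. The plan also has outcomes that do not condition on GVHD: SR GVHD, severe GI GVHD, non-relapse mortality, relapse and survival are compared in 11.3, and grade II-IV and III-IV incidence are secondary endpoints. A reader who sees fewer GVHD cases could work out why the response rate fell. Because AAT continues during GVHD treatment, how breakthrough GVHD responds to steroids plus AAT is also a fair clinical question.

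Most of this stands, and it limits the severity. It does not make the two GVHD subsets comparable. The clinical question is answered as well by a descriptive rate as by a comparison with controls selected differently.

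A reader might infer something stronger: that this comparison undermines the evidence for further study. The documents do not support that, because the go rule ignores the rate. A reader might also build a case in which AAT prevents only responsive GVHD. Per 100 patients, an assumed 60 GVHD cases with 28 refractory give 32/60 = 53%; preventing 16 responsive cases gives 16/44 = 36%. But SR GVHD then stays at 28%, which is the trial's null, and the go rule would fail with probability 1 − 0.224 = 0.776. The low response rate would agree with the primary result, so this does not show a conflict with it. The relevant test is the protocol's own effect, where reversal is conditional.

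**Conclusion.** The concern holds in a limited form. Section 11.3 plans a historical comparison in a subset that AAT is meant to alter, and nothing in the plan corrects for it. At the protocol's SR GVHD effect, the sign is wrong only if AAT cuts total GVHD by more than about 46% in relative terms; for smaller reductions it is right. The plan therefore supports saying that the comparison can mislead, not that it will.

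The threshold rests on the 28% and 15% in 11.2 and on the approximation that every GVHD case is steroid-treated and survives to day 28. The worked incidences are assumptions. The reach is one named secondary outcome, plus the GVHD-only measures in 11.1 if they too are compared under the open-ended list.

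**What to change.** In 11.3, state that the overall response rate, and the measures in 11.1 confined to subjects who develop GVHD (time to steroid discontinuation, number of lines of therapy), will be reported descriptively and not compared with historical controls. Give the numerator, denominator and, where applicable, an exact confidence interval, next to the incidence of GVHD needing systemic steroids.

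Replace the open-ended list with a closed one, limiting historical comparisons to outcomes not conditioned on developing GVHD: SR GVHD, grade II-IV and III-IV GVHD, stage 3-4 GI GVHD, non-relapse mortality, relapse and survival. Make these in the study's existing efficacy analysis set. Sections 5.1.5 and 5.9 already treat some non-compliant patients as inevaluable for efficacy and replace them, and this change need not reopen that.

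This is a cheap improvement: a short edit to one section, with no new data and no effect on sample size or the go rule. The downside is the loss of one benchmark comparison.

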## 12.0 DATA AND SAFETY MONITORING

The safety of subjects is paramount and supersedes all other concerns. This study employs several layers of oversight to ensure that patient safety is protected.

1. The local Data and Safety Monitoring Committee (DSMC) at each site which will be responsible for monthly reviews of patient data at each site
2. The Protocol Data and Safety Monitoring Committee (DSMC), composed of the individual site PI's which will review all facets of study conduct at all sites on monthly webinars
3. The Tisch Cancer Institute Data and Safety Monitoring Committee (TCI DSMC) of the Mount Sinai Health System is the DSMB of record for this study. The DSMB will be compliant with the NIH approved DSMP Charter. This committee will be responsible for monitoring the safety and data integrity of the trial. It is a DSMB entirely composed of members with no connection to this clinical trial.
4. Annual reviews and safety reporting will be provided to the IRBs at each participating site, the Mount Sinai Health System, and the FDA as required by IND regulations (21 CFR 312.3).

**Protocol DSMC:** The centers participating in this study are collaborating centers in MAGIC (Mount Sinai Acute GVHD International Consortium). The local site principal investigator, data manager, and study coordinator participates in monthly webinars where all facets of study conduct are discussed, thereby providing an additional layer of safety oversight.

The MAGIC Data Coordinating Center is responsible for collating all data and safety reports from all the participating sites, and providing the information to the TCI Data Safety Monitoring Committee.

**TCI DSMC:** The TCI DSMC serves as the data and safety monitoring board (DSMB) for investigator initiated studies conducted under the auspices of the Tisch Cancer Institute (TCI) at the Mount Sinai Health System. It is compliant with the National Institutes of Health and National Cancer Institute charter for DSMBs. This board will be responsible for monitoring the safety and data integrity of the trial. It is a DSMB entirely composed of members with no connection to this clinical trial.

## **12.1 Multisite Clinical Monitoring Procedures**

This clinical study will be coordinated by the MAGIC Data Coordinating Center (DCC) of the Icahn School of Medicine at Mount Sinai. As such it will be conducted in accordance with the ethical principles that are consistent with Good Clinical Practices (GCP) and in compliance with other applicable regulatory requirements.

Prior to subject recruitment, a participating site will undergo a site initiation meeting to be conducted by the DCC. This will be done as an actual site visit, teleconference, videoconference, or web-based meeting after the site has been given access to the study database and assembled a study reference binder. The site's principal investigator and his/her study staff should make every effort in attending the site initiation meeting. Study-related questions or issues identified during the site initiation meeting will be followed-up by the appropriate DCC personnel until they have been answered and resolved.

This study will be monitored by a representative of the MAGIC Data Coordinating Center. Monitoring visits, whether remote or in person, will be made during the conduct of the study and at study close-out. The following issues will be monitored.

- Signed and dated ICF
- Adherence to the protocol
- Completeness and accuracy of study data and laboratory samples collection
- Proper storage, dispensing and inventory control of investigational drug
- Compliance with state and local regulations

Any issues identified during these visits will be communicated to the site and are expected to be corrected by the site in a timely manner. For review of study-related documents at the DCC, the site will be required to ship, fax, or email documents to be reviewed, ensuring compliance with HIPAA and other privacy regulations.

Participating sites will also undergo a site close-out upon completion, termination or cancellation of a study to ensure fulfillment of study obligations during the conduct of the study, and that the site Investigator is aware of his/her ongoing responsibilities. In general, a site close-out is conducted during a site visit; however, site close-out can occur without a site visit if all of the following apply:

- No patient has signed the Informed Consent Form and has enrolled into the study
- Investigational agent has not been dispensed
- All investigational agent and materials have been returned as defined for the study or destroyed and accounted for properly.

## **13.0 QUALITY ASSURANCE AND AUDITS**

The Data Safety Monitoring Board can request a 'for cause' audit of the trial if the board identifies a need for a more rigorous evaluation of study-related issues. A "for cause" audit would be conducted by the Project Manager of the MAGIC Data Coordinating Center.

A regulatory authority (e.g. FDA) may also wish to conduct an inspection of the study, during its conduct or even after its completion. If an inspection has been requested by a regulatory authority, the site investigator must immediately inform the MAGIC Data Coordinating Center that such a request has been made.

## 15.0 APPENDICES

**Appendix A:** High Risk MAGIC Scoring Manual

**Appendix B:** BMT CTN Infection Severity Grading Table

**Appendix C:** Suggested Steroid Taper for GVHD
